There is only one treatment condition: i.e. children and their non-abusive parent will receive BB4K sessions. In total 40 parent–child pairs referred to BB4K will be assigned to the treatment group. Parents and children recruited in Cohort 1 and assigned to the treatment condition (i.e. 16 parent–child pairs) will receive BB4K sessions between May and July 2024, while those recruited in Cohort 2 and assigned to the treatment arm (i.e. 24 pairs) will receive BB4K sessions between September and December 2024.

A total of 32 parent–child pairs will be assigned to the waitlist treatment. They will be given access to the new digital platform, ‘Bounce’, in addition to the business as usual support they are receiving from other services, before they receive the BB4K support (see ‘Business as usual’ for more information on the additional support offered). For this evaluation, that means that we are assessing the effect of the group sessions rather than the full package of support offered as part of BB4K which includes ‘Bounce’ (but is not required for all BB4K families to use). This has the benefits of offering a support to the waitlist group and may improve retention in the waitlist treatment group.

Given that the delivery of BB4K will take place sequentially in two cohorts, randomisation will occur at two different time points (see ‘Randomisation’ for more information).

[figure not shown]
Trial type and number of arms		Two-arm, cohort, randomised waitlist trial
Unit of randomisation		Parent–child pairs (family level)
Block (stratification) variables		Delivery site (age ⁷)
Primary outcome	variable	Parents’ self-efficacy
	measure (instrument, scale)	Tool of Parental Self Efficacy (A multi-dimensional parent self-report of 48 statements within 8 scales measuring parental self-efficacy. The score ranges between 0 and 60.)
	variable(s)	
 1. Children’s behavioural issues at home 2. Parent–child relationship and bonding

⁷ Relevant for Cohort 2 only, as only children between 6 and 11 will take part in Cohort 1.

Secondary outcome(s)	measure(s) (instrument, scale)	
1. Brief Assessment Checklist for Children (20 items parent self-report screening and monitoring scale. The total score is between 0 and 40)2. Child Parent Relationship Scale – closeness scale (Parent self-report, 10 items, ranging between 10 and 50)
-----------------------------	---	---

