The diagram below shows the participants' journey through the trial.

Randomisation

As BB4K is a group-based programme, randomisation will be executed in blocks according to children's age and stratified by site. Allocation into treatment or waitlist control will be done at the parent-child level. Randomisation of children-parent pairs will be undertaken after families have been referred to BB4K and informed consent has been provided. Randomised blocks will be used at each delivery site to allocate participants to either treatment or waitlist treatment groups.

Randomisation will occur at two different time points for Cohort 1 and 2, as follows:

Randomisation for Cohort 1 (scheduled for Apr 2024): Once parents and children in Cohort 1 are recruited they will be randomised to either receive BB4K immediately, i.e. between May and July 2024, or to be allocated to the waitlist treatment group who will receive BB4K 8 months after the treatment group, i.e. in January 2025. In total, 32 parent-child pairs will be randomised to two treatment and two waitlist treatment groups. Given that group delivery is organised regionally, with key covariates likely to vary across delivery sites, stratifying by delivery site ensures the treatment and waitlist treatment are balanced across sites. Groups will be blocked on the age of the children with age bandings: 6–8, and 9–11.

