Randomisation for Cohort 2 (scheduled for Sep 2024): Parents and children from Cohort 2 will be randomised to the treatment condition, i.e. to receive BB4K immediately in Sep 2024, or to the waitlist treatment condition, who will receive the intervention 5 months after the treatment groups, i.e. in March 2025. Up to 40 parent-child pairs will be recruited in Cohort 2 and this cohort will also include children aged 3–5. There will be up to 16 families with children aged 3–5, and up to 24 families with children aged 6–11. Half of the families with younger children (3–5) will be allocated to the treatment, and the remaining half to the waitlist treatment. Families with children aged 6–11 will be allocated to the treatment and waitlist treatment condition with 2:1 assignment, i.e. 16 parent-child pairs will be allocated to the treatment group, and 8 parent-child pairs will be allocated to the waitlist treatment group. Parent-child pairs will be stratified by region and on whether they are eligible for the younger or older group based on the child's age classification prior to randomisation. This will ensure balance across treatment and waitlist treatment arms across sites and younger/older groups after randomisation.

It is important to note that the transition period for the waitlist treatment group is long, particularly for the waitlist treatment in Cohort 1. The timeline was selected to accommodate PACT's capacity for delivery (maximum two or three groups) and to enable outcomes to emerge (i.e. the timeline is designed to allow two months between endline and follow-up data collection).

The differential waitlist times has the potential to introduce a number of biases that could impact the validity and reliability of the findings. Cohort 1 waitlist participants who have to wait three months longer (8 months compared to Cohort 2's 5 months) to receive the programme may be more likely to drop out of the study. Likewise, longer waiting times might affect participants' expectations or motivation regarding the programme. Additionally, those with a longer waitlist time may experience changes over time, like an improvement or worsening of outcomes, or may be more likely to seek additional support which could confound the effects of the programme.

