The primary outcome is the TOPSE score at follow-up,¹⁸ controlling for baseline TOPSE score. We will estimate the mean difference in TOPSE scores between participating families in BB4K and the waitlist treatment group participants. The primary analysis will use a mixed effects model allowing for different outcome variance between the treatment group and waitlist treatment group arms, and heteroscedastic individual-level errors. The model will control for delivery site, child age,¹⁹ and baseline TOPSE score via fixed effects. The between-cluster variation in the treatment group groups will be modelled as a random effect. The model is not powered to investigate differences in treatment effects between sites.

The analysis model will be:

$$Y_{ijk} = \beta_0 + \sum_{k=1}^3 \beta_k s_k + \gamma Y_{0ijk} + \delta X_{ijk} + \theta t_{ijk} + t_{ijk} u_{jk} + (1 - t_{ijk}) r_{ijk} + t_{ijk} \varepsilon_{ijk}$$

- Y_{ijk} is the outcome at follow up for parent i in treatment group j and sites k
- There are three sites $k= 1,2,3$
- There are $j=9$ clusters corresponding to 5 treatment group and 4 waitlist treatment groups
- Sites $k=1,2,3$
- β_k represents difference in outcomes between sites
- θ is the treatment effect.

In line with Foundation's Statistical Guidance, the analyses will follow an intention-to-treat (ITT) approach. The analysis will include all randomised children and parents in the groups to which they were randomly assigned, regardless of the treatment actually received, withdrawal from BB4K post-randomisation, or deviations in programme implementation. This principle is key in ensuring an unbiased analysis of intervention effects. The difference between the treatment and waitlist treatment groups at endline will be expressed as a standardised effect size using Hedges' g with 95% confidence intervals. The primary analysis will also include detailed descriptive analysis: histograms, means, quartiles, and standard deviations, for all measures, groups, and time points. All analysis will be scripted to allow for transparency and replication and will be uploaded to GitHub.

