Outcome measures are not optimal	Low/Medium	Outcome measures do not align with the theory, are difficult to administer, or measure a change that cannot be realised within the timeline.	Our experienced team will ensure that outcome measures are fit for purpose. This includes expert assessment and consultations with PACT to allow us to select the most robust instruments.

Timeline

Dates	Activity	Staff responsible/ Leading
January to April 2024	Onboarding and set-up (including evaluation protocol, ethics and data protection)	IFF Research
April to May 2024	Cohort 1 delivery set-up, randomisation and baseline survey (2 research/treatment groups and 2 non-research/waitlist treatment groups)	IFF Research/PACT
May to July 2024	Cohort 1 group delivery (2 groups of aged 6-11s) – 8 sessions over 10 weeks	PACT
July 2024	Cohort 1 endline survey	IFF Research
June to August 2024	Implementation and process evaluation Wave 1	IFF Research
September to October 2024	Cohort 1 follow-up survey	IFF Research
January to March 2025	Cohort 1 waitlist treatment group delivery	PACT
August to September 2024	Cohort 2 delivery set-up, randomisation and baseline survey (3 research/treatment groups and 2 non-research/waitlist treatment groups)	IFF Research/PACT
August 2024	Cost evaluation data collection Wave 1	IFF Research
September to December 2024	Cohort 2 group delivery (2 groups of aged 5–11s; 1 group age 3–5)	PACT

December 2024	Cohort 2 endline survey	IFF Research
November 2024	Mid-point grant progress report	IFF Research
December 2024 to January 2025	Implementation and process evaluation Wave 2	IFF Research
January to March 2025	Interim report	IFF Research
March 2025	Cohort 2 follow-up survey	IFF Research
April 2025	Cost evaluation data collection Wave 2	IFF Research
May to September 2025	Final reporting	IFF Research

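### Footnote 7 to the design table limits age as a stratification factor to Cohort 2, against the Randomisation section, its table and footnote 19, which block Cohort 1 on age as well

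*Protocol*

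**What the plan says.** The design table in the Protocol (Impact evaluation, Design) gives the block (stratification) variables as delivery site, with age in brackets. Footnote 7 qualifies the age entry: "Relevant for Cohort 2 only, as only children between 6 and 11 will take part in Cohort 1".

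The Randomisation section opens with a rule that has no cohort limit: "randomisation will be executed in blocks according to children's age and stratified by site". Under Cohort 1 it says that "32 parent-child pairs will be randomised to two treatment and two waitlist treatment groups", and then "Groups will be blocked on the age of the children with age bandings: 6–8, and 9–11". The summary table in the same section shows one 6–8 group and one 9–11 group in each arm of Cohort 1, at 1:1.

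For Cohort 2 the strata are region and younger/older group. Up to 16 families with children aged 3–5 are split in half. For up to 24 older families, "Families with children aged 6–11 will be allocated to the treatment and waitlist treatment condition with 2:1 assignment", giving 16 and 8. The summary table shows the cohort total as 3:2.

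The Primary analysis section says "The model will control for delivery site, child age" and baseline TOPSE through fixed effects. Footnote 19 justifies the age term by stratification on region and age, again without a cohort limit. The Timeline has a delivery row reading "Cohort 2 group delivery (2 groups of aged 5–11s; 1 group age 3–5").

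**The concern.** Stratification factors define the randomisation list, so a protocol should state them once and the same way throughout. Read literally, footnote 7 has Cohort 1 randomised within site only, while the Randomisation section has it randomised within site and age band. Both cannot describe the same list.

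Two things depend on which is right. The first is what the report will say was done for 32 of the 72 pairs. The second is the age term in the primary model, whose stated justification is that age was a blocking factor. That term should reflect the strata used, particularly as the allocation ratio is not the same in all of them.

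**Working it through.** **1. Reproduce the stated totals.** Group size is eight pairs (Sample size/MDES calculations).
- Cohort 1: 2 × 8 = 16 treatment and 2 × 8 = 16 waitlist.
- Cohort 2: 16/2 + 24 × 2/3 = 8 + 16 = 24 treatment; 16/2 + 24/3 = 8 + 8 = 16 waitlist.
- Sum: 40 and 32, total 72. The Cohort 2 ratio 24:16 is 3:2.

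All figures agree with the protocol. The inconsistency is in the factors, not the counts.

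**2. Set the Cohort 1 statements side by side.**

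| Place | Is age a factor in Cohort 1? |
|---|---|
| Design table, footnote 7 | No |
| Randomisation, opening rule | Yes, no cohort limit |
| Randomisation, Cohort 1 paragraph | Yes, 6–8 and 9–11 |
| Randomisation, summary table | Implied: one group of each band per arm |
| Primary analysis, footnote 19 | Yes, no cohort limit |

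Footnote 7 argues from Cohort 1 containing only children aged 6–11. That shows that the 3–5 versus 6–11 factor is constant there. It says nothing about 6–8 versus 9–11.

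**3. How the two lists differ.** With three sites, site alone gives up to 3 strata of about 32/3 = 10.7 pairs. Site by two age bands gives up to 6 strata of about 32/6 = 5.3 pairs.

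**4. Does blocking affect the planned groups?** The documents do not give band sizes. Assume 16 children per band, 16:16 allocation and no site stratification. Without age blocking, the number of 6–8s in the treatment arm is hypergeometric:
- P(exactly 8) = C(16,8)² / C(32,16) = 0.276
- P(7, 8 or 9) = 0.711
- P(10:6 or more uneven) = 1 − 0.711 = 0.289

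Blocking secures the even split and its absence does not. These figures are illustrative only.

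**5. Why the coding of the age term matters.** Treatment shares by stratum are 16/32 = 0.50 in Cohort 1, 8/16 = 0.50 in Cohort 2 aged 3–5, and 16/24 = 0.67 in Cohort 2 aged 6–11. Children aged 6–11 therefore occur at two different ratios. Of the 16 + 16 = 32 older treatment pairs, 16/32 = 50% are from Cohort 2. Of the 16 + 8 = 24 older waitlist pairs, 8/24 = 33% are. The difference is 1/6.

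A term for child age alone does not separate these strata. Suppose the follow-up outcome, given baseline, differs by *d* SD between the cohorts at those ages. The contrast among older families then shifts by about *d*/6. The protocol gives no value for *d*. For assumed values of 0.1, 0.3 and 0.5 the shift is 0.02, 0.05 and 0.08 SD, against a stated MDES of 0.79.

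**6. Age 5 in the Timeline.** A 5-year-old has treatment probability 1/2 in the 3–5 stratum and would have 2/3 in a 5–11 stratum. If *m* of the 16 younger families moved, expected treatment numbers would be (16 − *m*)/2 + (24 + *m*) × 2/3 = 24 + *m*/6, which is 24.3 for *m* = 2 and 25.3 for *m* = 8.

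**The case against.** The best defence is that footnote 7 is about the younger/older factor only. On that reading it is correct as far as it goes, and the summary table merely omits a further banding that the Randomisation section supplies. The Design section refers the reader there for detail. This stands as the likely explanation, and it makes the defect an error in one place rather than an undecided design. It does not make the table right: a reader who relies on it would take Cohort 1 to be stratified by site alone.

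A second defence is that Cohort 1 blocking only means forming delivery groups after allocation. This is weak. The design table treats blocking and stratification as the same thing, and the Randomisation section says that randomisation itself is carried out in age blocks.

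A third is that allocation is random and the model adjusts for site and age under either reading. That is largely true, and step 5 of the working shows that any distortion is small.

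A reader might infer three stronger points, none of which the documents support.
- *That the planned groups would fail to form in 72% of randomisations.* This takes 1 − 0.276 and treats eight as a strict size, which no section requires. The numbers are maxima, the delivery section gives the bandings as examples, and the age and location distribution is to be examined before randomisation. A 7/9 split differs from plan by one family.
- *That the Timeline moves the Cohort 2 cut-off.* It keeps the 3–5 group, so it only creates an overlap at age 5. It is a delivery row, and the Randomisation text and table agree on 3–5 and 6–11.
- *That 3:2 is wrong.* It is the correct pooled ratio, and the text gives both stratum ratios.

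**Conclusion.** The contradiction is real and confined to one place. Footnote 7 excludes age as a Cohort 1 factor, while the opening randomisation rule, the Cohort 1 paragraph, the summary table and footnote 19 state or imply the opposite. It bears on how 32 of the 72 pairs are randomised (up to 3 strata or up to 6) and on the stated reason for the age term. It does not alter the sample size or the allocation totals, and it does not by itself show bias.

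The effect on inference is modest. It rests on the age term being coded without regard to cohort and on an assumed outcome difference between cohorts. Coding the strata correctly removes it at no cost. The age-5 overlap is secondary, worth *m*/6 pairs in expectation, and arises only if the list were built from the Timeline row.

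**What to change.** Amend the design table and footnote 7 to match the Randomisation section:
- Cohort 1: delivery site and age band (6–8, 9–11), 1:1.
- Cohort 2: delivery site and younger/older stratum, at the 1:1 and 2:1 already stated.

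In the Primary analysis section, define the age term as these randomisation strata, so that Cohort 1 and Cohort 2 families with children aged 6–11 are distinguished, and keep footnote 19 consistent with that. Reconcile the 5–11 entry in the Timeline with the bands in the Randomisation section so that a 5-year-old falls in one stratum only.

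If the Cohort 1 list has already been generated, record which rule was used and code the model to it. The cost is protocol wording and one line of model specification, with no extra families, data or delivery changes.

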Given that PACT collects TOPSE (parental self-efficacy) as part of usual practice, they will collect the questionnaire from participating parents and will share the data with IFF, while IFF research will collect data on the secondary outcome measures (i.e. BAC-C and CPRS) from participating parents through parent-administered surveys. This approach has been taken to keep data collection from participants as minimal as possible in line with ethical good practice.

Parents will be given the questionnaire to fill in on their own without PACT present.

The researchers scoring the data will not be blind to intervention allocation. If the parent reveals their allocated treatment group to the researcher, this will be recorded.

The baseline and follow-up surveys will be sent via email and IFF will follow-up with reminder emails and telephone calls. Parents in the treatment group will complete the endline survey in the final session. PACT will extend the last session by 15 minutes to give parents time to complete the survey. Parents will be encouraged to complete the survey on their own device (e.g. their phone), but PACT will provide an alternative if needed (e.g. using a PACT laptop). Parents and children in one of the Cohort 1 waitlist treatment groups will complete the endline survey during an in-person event (for more information on the event please see the [Experiment 1: Testing use of in-person events](#)). For groups not involved in-person experiment events, parents will be sent the surveys via email by IFF to complete.

The study acknowledges that the different approaches to outcome measure deployment between the treatment group and the waitlist treatment group has the potential to introduce different biases. Though PACT may not be present, the treatment group's TOPSE being organised by PACT for the baseline and endline still may influence responses, for example by increasing the likelihood of socially desirable answers. Conversely, the waitlist treatment group receiving all measures via email may increase the potential of experiencing technical issues filling in the survey or not being able to ask for clarity on questions as they will not be in regular contact with PACT.

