To limit the effect of these factors, anonymity and confidentiality are emphasised in communication with participants, and clear standardised instructions are provided. Likewise, feedback on the experience of using the surveys will be collected as part of the study and a review of selected outcome measures will occur between Cohort 1 and Cohort 2 (for details, see the following section).

Cohort 1 parent–child pairs will complete the baseline survey between April and May 2024, the endline between July and August 2024, and the follow-up between September and October 2024. Cohort 2 parent–child pairs will complete the baseline survey in September 2024, the endline between December 2024 and January 2025, and the follow-up survey between February and March 2025.

	Cohort 1		Cohort 2	
	Treatment (2 groups)	Waitlist treatment (2 groups)	Treatment (3 groups)	Waitlist treatment (2 groups)
Baseline survey	Apr–May 24	Apr–May 24	Sep 24	Sep 24
Delivery	May–Jul 24 (2 groups)	Jan–Mar 25 (2 groups)	Sep–Dec 24 (3 groups)	Mar–May 25 (2 groups)
Endline survey	Jul–Aug 24	Jul–Aug 24	Dec 24–Jan 25	Dec 24–Jan 25
Follow-up survey	Sep–Oct 24	Sep–Oct 24	Feb–Mar 25	Feb–Mar 25

Review of outcome measures before they are used with Cohort 2

It is important to note that measuring outcomes for children and young people who have experienced domestic abuse can be a challenging task. While the selected measures have been used with a general population, these are not validated specifically for this group. Therefore, we will review the suitability of using the secondary outcome measures with Cohort 1. As part of this, we will review the ease of administration of the self-report surveys, including take up and time needed for administration with Cohort 1. We will also assess whether the scores are normally distributed.

Following the review, a decision will be made on whether we will employ the same outcome measures with Cohort 2.

Analysis plan

The Statistical Analysis Guidance produced by What Works for Children’s Social Care is still applicable for the work of Foundations.¹⁷

Primary analysis

The pilot is designed as a cohort two-armed, randomised waitlist trial.

¹⁷ See <https://whatworks-csc.org.uk/wp-content/uploads/WWCSC-RCT-Statistical-Analysis-Guidance-V1.2.pdf>

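### The protocol does not fix baseline TOPSE before allocation and contradicts itself on how it is collected, so the covariate in the primary model could depend on arm

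*Protocol*

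**What the plan says.** **Order.** The Randomisation section sets two preconditions, referral and informed consent. A completed baseline is not one of them. The eligibility list under Participants asks for willingness to complete questionnaires at three time points, which is not the same as having completed the first. After randomisation the delivery team tells families their allocation.

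**Dates.** The Randomisation section has "Randomisation for Cohort 1 (scheduled for Apr 2024" and "Randomisation for Cohort 2 (scheduled for Sep 2024"; its summary table gives April to May and August to September. Under Data collection, "Cohort 1 parent–child pairs will complete the baseline survey between April and May 2024", and Cohort 2 "pairs will complete the baseline survey in September 2024". Cohort 2 treatment groups also start BB4K in September. The Timeline has one row per cohort for these steps; Cohort 2's reads "Cohort 2 delivery set-up, randomisation and baseline survey".

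**Mode.** Data collection first says that PACT will collect TOPSE from participating parents, without naming an arm. It then says: "The baseline and follow-up surveys will be sent via email and IFF will follow-up with reminder emails and telephone calls", again without naming an arm. Later, writing of the treatment group, it concedes that "TOPSE being organised by PACT for the baseline and endline still may influence responses", with socially desirable answers as the example. It contrasts this with a waitlist group that receives every measure by email.

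**Use.** Primary analysis enters baseline TOPSE as a fixed effect. The Randomisation section attributes any baseline imbalance to chance.

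**The concern.** Adjusting for a baseline score is safe in a randomised trial because the score cannot have been affected by allocation. That guarantee fails if parents know their arm when they answer, or if the arms answer in different ways. Relief, disappointment or a wish to please the provider could then move baseline TOPSE in one arm only, and the adjustment would carry that movement into the treatment effect. A difference between arms in baseline TOPSE could also no longer be put down to chance.

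Follow-up, the primary time point, is described as emailed to both arms, apart from the Cohort 1 event experiment, which takes one group from each arm. A mode effect present only at baseline would therefore not be expected to cancel. Analysis cannot later recover a pre-allocation baseline that was never taken.

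**Working it through.** **1. Does the text fix the order?**

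| | Randomisation | Baseline survey | Treatment delivery starts |
|---|---|---|---|
| Cohort 1 | Apr 2024 (text); Apr–May (table) | Apr–May 2024 | May 2024 |
| Cohort 2 | Sep 2024 (text); Aug–Sep (table) | Sep 2024 | Sep 2024 |

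The windows overlap in both cohorts. The dates allow baseline before, during or after allocation, and no sentence in the available text settles it.

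**2. Does the text fix the mode?** The general sentences (PACT collects TOPSE; baseline goes by email) make no distinction by arm. The later sentences do: PACT organises it for treatment, email for waitlist. These cannot both describe baseline TOPSE, and the second presupposes known allocation.

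**3. The plan's own precision figure.** Inputs from Sample size/MDES calculations: P = 40/72, J = 9 clusters of n = 8, group ICC 0.1 (table), correlation 0.56 (so R² = 0.3136, applied at individual level only), 80% power, two-sided 5%.

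MDES = (1.960 + 0.842) × √[0.1/(P(1−P)J) + 0.9 × 0.6864/(P(1−P)Jn)]
= 2.802 × √[0.1/2.222 + 0.6178/17.78]
= 2.802 × √(0.0450 + 0.0347) = 0.791

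This reproduces the stated 0.79. The implied standard error is 0.79/2.802 = 0.282 SD. (The text's ICC of 0.01 gives 0.579 instead; that discrepancy is a separate matter.)

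**4. Bias from an arm-dependent baseline.** Let the treatment-arm baseline be shifted by d SD and a fraction p of that shift persist at follow-up. With slope γ = 0.56 (the plan's correlation, equal SDs assumed):

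bias = p·d − γ·d = d(p − 0.56)

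The documents give no value for d or p, so the rows below are assumptions. The power and type I error columns use the 0.282 standard error and p = 0.

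| d (SD) | Bias, p = 0 | Share of 0.79 | Power at 0.79 | Type I error | Bias, p = 1 |
|---|---|---|---|---|---|
| 0 | 0 | 0% | 80% | 5.0% | 0 |
| 0.1 | −0.056 | 7% | 74% | 5.5% | +0.044 |
| 0.2 | −0.112 | 14% | 67% | 6.8% | +0.088 |
| 0.3 | −0.168 | 21% | 60% | 9.2% | +0.132 |

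Simulation of 4,000 trials of 40:32 gave −0.112 (d = 0.2, p = 0), −0.167 (d = 0.3, p = 0) and +0.133 (d = 0.3, p = 1), which agrees with the formula. A downward shift reverses every sign. For a given shift the sign also changes once p exceeds 0.56.

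**The case against.** A reader might infer that baseline is scheduled after randomisation. The documents do not support that. On some of the stated dates the windows coincide exactly (April to May; September), which fits baseline first equally well. The Timeline entry is a single activity row, so its word order is not a sequence. Requiring consent before randomisation does not exclude a prior baseline. The participant-journey diagram is not in the available text and may state the order. A baseline taken after Cohort 2 sessions begin is likewise only a possibility raised by the shared month.

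A reader might also take it as settled that treatment-arm baseline is run by PACT and waitlist baseline by email. That is one side of a contradiction; the same section also describes emailed baselines for everyone, and says parents complete the questionnaire without PACT present.

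The protocol does disclose the mode bias and offers mitigations: confidentiality messages, standard instructions, feedback on the surveys and a review of measures between cohorts. It also plans multiple imputation for covariates with more than 5% and less than 40% missing. The mitigations deserve credit, but none puts baseline before allocation, and none addresses the role of baseline TOPSE as a covariate.

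Finally, the shifts are assumed, and biases of 0.056 to 0.168 SD are only about 0.2 to 0.6 of a standard error in a 72-pair pilot. That limits the severity. The gap remains, because the pilot estimates effects to judge evidence of promise and tests the design for a larger trial.

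**Conclusion.** The point holds as a gap and a contradiction. The protocol permits, but does not prescribe, a baseline TOPSE taken after allocation and in a mode that differs by arm, and the primary model conditions on that score. If a shift arises in the treatment arm only and fades by follow-up, the bias is about −0.56 times the shift: −0.11 SD for an assumed +0.2 SD, with power at 0.79 SD falling from 80% to about 67%. This assumes a slope equal to the plan's correlation and equal SDs at both time points.

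No definite size or direction can be claimed. An upward, socially desirable shift that fades works against BB4K; a downward one works in its favour; persistence to follow-up can reverse either. The premise that imbalance is due to chance is weakened for baseline TOPSE only. Site and child age are unaffected. Severity is moderate.

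**What to change.** - In the Randomisation, Data collection and Timeline sections, state that baseline TOPSE, and preferably BAC-C and CPRS, is collected after consent and before allocation is generated or disclosed.
- State that baseline TOPSE has the same collector and mode in both arms. Either PACT or IFF would do, so PACT's routine TOPSE collection can be kept if it applies equally to both arms.
- Reconcile the Data collection sentences on who collects baseline TOPSE and how.

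The cost is wording, resequencing within the existing windows, some reminders and possibly a short delay to randomisation. A completed baseline need not be an entry condition, which matters because low response is already a listed risk and groups of eight must be filled. Families without a baseline can still be randomised, with the missing score handled under the existing covariate imputation rule rather than collected after allocation.
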